Local infiltrative analgesia administered by the surgeon around the joint capsule has been an emerging adjunct to multimodal analgesia advocated by surgeons claiming improved rehabilitation by reducing venous stasis and maximizing motor strength. Periarticular analgesia (PAI) primarily targets the mechanoreceptors and the free nerve endings in the intra articular area.

 Mount Sinai	Protocol Name:	COMPARISON BETWEEN IPACK BLOCK AND PERIARTICULAR INFILTRATION IN TOTAL KNEE ARTHROPLASTY - A RANDOMISED CONTROLLED TRIAL
	Principal Investigator:	[name] [name].
	Primary Contact Name/Contact Info:	[name] MD. [REDACTED]
	Date Revised:	7/22/2017
	Study Number:	IF# 2087568 , GCO#17-04304

IPACK block is a novel technique gaining popularity where one injects local anesthesia safely under ultrasound guidance in the interspace between the popliteal artery and capsule of the knee. It primarily targets genicular nerves innervating the knee joint. It does not affect the sciatic nerve hence motor blockade is avoided promising enhanced recovery.

There have been no studies till date comparing the efficacy between IPACK block and PAI.

The purpose of our study is to evaluate the difference in quality of analgesia between efficacy of IPACK block and PAI performed by surgeon as measured by patient's opioid consumption and pain scores.

1) Objectives

Research Question: Does IPACK block provide superior analgesia in comparison with surgeon performed periarticular infiltrate (PAI) in TKA patients?

Primary outcome: The amount of opioid consumption (in mg IV morphine equivalents) postoperatively during the first 24 hours after the procedure. VAS pain scores on arrival and departure from PACU.

Secondary outcome:

The degree of postoperative pain in terms of VAS scores from arrival to the floors to the first 24 hours after surgery.

Time to first dose of narcotic administration, PACU length of stay, location of pain, ambulation distance with assistance on POD 1 as assessed by PT and activities of daily living(ADL's) on POD 1 as assessed by OT.

2) Background

See above. There have been several studies regarding efficacy of peri-articular infiltration. IPACK block is a novel technique gaining popularity where one injects

 Mount Sinai	Protocol Name:	COMPARISON BETWEEN IPACK BLOCK AND PERIARTICULAR INFILTRATION IN TOTAL KNEE ARTHROPLASTY - A RANDOMISED CONTROLLED TRIAL
	Principal Investigator:	[name] [name].
	Primary Contact Name/Contact Info:	[name] MD. [REDACTED]
	Date Revised:	7/22/2017
	Study Number:	IF# 2087568 , GCO#17-04304

local anesthesia safely under ultrasound guidance in the interspace between the popliteal artery and capsule of the knee.

There have been no studies till date comparing the efficacy between IPACK block and PAI.

3)Setting of the Human Research

Prospective triple blinded randomized control trial undergoing total knee arthroplasty surgeries. The research study will take place at Mount Sinai West hospital and Mount Sinai St. Luke's hospitals. The site PI is [name], MPH.

4)Resources Available to Conduct the Human Research

For n=200, the feasibility of recruitment is manageable. Recruitment will be done through a coordination of the operating schedule and the surgeon's office. Patients presenting for preoperative visits at the preoperative joint clinic will be approached. Patients routinely are seen by anesthesiologists at the pre operative testing clinic as part of pre operative anesthetic evaluation. Patients will be approached by research personnel and details of the study will be explained. The consent will be obtained in the pre operative testing clinic after all questions are thoroughly answered. After confirmation on the operating schedule, patients will be provided detailed instructions the day before surgery. The staff members on this protocol are all employees of Mount Sinai and will either be a resident or attending physicians that are included on the IRB protocol. There are two primary members of the research personnel:

a)[name], MPH – Roles for [name] in this study include serving as primary investigator responsible for study design and planning, data collection, subject recruitment, manuscript writing and preparation, data analysis, safety monitoring, and responding to adverse events and/or complications. He is certified in PPHS/IRB protocols, all Citi/IRB required training in human subject protection, and has prior clinical research experience. He is also a board certified anesthesiologist and assistant professor of anesthesiology with the Icahn School of Medicine and the Mount Sinai Health System.

 Mount Sinai	Protocol Name:	COMPARISON BETWEEN IPACK BLOCK AND PERIARTICULAR INFILTRATION IN TOTAL KNEE ARTHROPLASTY - A RANDOMISED CONTROLLED TRIAL
	Principal Investigator:	[name] [name].
	Primary Contact Name/Contact Info:	[name] MD. [REDACTED]
	Date Revised:	7/22/2017
	Study Number:	IF# 2087568 , GCO#17-04304

b) [name] MD – Roles for [name] include serving as primary research coordinator involved in data collection, subject recruitment, manuscript writing and preparation, data analysis, safety monitoring, and responding to adverse events and/or complications. She has completed all of her required CITI training to be IRB certified and has experience in clinical research. In addition she has been a resident physician in anesthesiology with the Icahn School of Medicine in good standing for the previous three years going on her fourth.

There are institutional processes to ensure that all persons assisting with the protocol will be well informed. The research personnel will conduct regular meetings and department email updates to review the results and safety data of the study. The research personnel will initiate the formation of a safety monitoring board for adverse effects, complications, or complaints from patient subjects.

5) Study Design

Prospective triple blinded randomized control trial. Recruitment will be done through a coordination of the operating schedule and the surgeon's office. Patients presenting for preoperative visits at the preoperative joint clinic will be approached. Patients routinely are seen by anesthesiologists at the pre operative testing clinic as part of pre operative anesthetic evaluation. Patients who meet the inclusion criteria will be approached by research personnel and details of the study will be explained. The consent will be obtained in the pre operative testing clinic after all questions are thoroughly answered. The team will finalize participation and ask the subject to sign study consent forms. All patients will be provided with copies of the IRB protocol and consent if they wish to have it. Copy of the consent form will be sent in a secured email to the potential subject. The email will be secured by entering in [SECURE] in the e-mail subject line. Once recruited blinding assessments will be done by the study team.

Patients will be assigned randomly using a computer- generated table of numbers to either IPACK block (IPACK group) or Periarticular infiltration (PAI group). Block team will perform all blocks. Resident anesthesiologist will know the group allocation but will not be involved in the study. Patients assigned to IPACK block group will receive 20cc 0.25% bupivacaine under USG guidance on the side of

 Mount Sinai	Protocol Name:	COMPARISON BETWEEN IPACK BLOCK AND PERIARTICULAR INFILTRATION IN TOTAL KNEE ARTHROPLASTY - A RANDOMISED CONTROLLED TRIAL
	Principal Investigator:	[name] [name].
	Primary Contact Name/Contact Info:	[name] MD. [REDACTED]
	Date Revised:	7/22/2017
	Study Number:	IF# 2087568 , GCO#17-04304

surgery. At the conclusion of the surgery prior to skin closure, all patients in the PAI group will receive 100cc of joint cocktail infiltrated by the surgeon. Patients in both groups will receive a post operative adductor canal catheter in the PACU, with Bupivacaine 0.1% 8-12 cc/hr with demand dose of 3-5 cc q20 min. Otherwise, the patient, surgeon, and anesthesiologist in the case will be blinded.

a) Recruitment methods: Patients will be recruited and consented in pre operative testing/Joint clinic.

b) Inclusion and Exclusion Criteria

Inclusion criteria: ASA (American Society of Anesthesiology) class I-IV, age 18-75.

Exclusion criteria: ASA class V, morbid obesity, patient refusal, patients with chronic pain or on pain medications, allergy to LA, patients receiving any additional regional techniques, coagulopathy, patients receiving systemic anticoagulation, local infection, and procedures anticipated to last more than 5 hours.

c) Number of Subjects

We intend to recruit 200 patients.

Based on a confidence level of 99% with a Z score of 2.58, standard deviation of .5 and a confidence interval of 10% our sample size should be 166. For ease of statistical calculations we rounded up to 200 patients. Based on previous literature pertaining to local articular infiltration in total knee arthroplasty and postoperative femoral nerve block, we found studies included anywhere from 40 to 100 patients. We intend to use a higher sample size to see any statistical significance.

$$Z^2 * (p) * (1-p)$$

ss = _____

$$c^2$$

Where:

 Mount Sinai	Protocol Name:	COMPARISON BETWEEN IPACK BLOCK AND PERIARTICULAR INFILTRATION IN TOTAL KNEE ARTHROPLASTY - A RANDOMISED CONTROLLED TRIAL
	Principal Investigator:	[name] [name].
	Primary Contact Name/Contact Info:	[name] MD. [REDACTED]
	Date Revised:	7/22/2017
	Study Number:	IF# 2087568 , GCO#17-04304

Z = Z value (2.58 for 99% confidence level)

p = percentage picking a choice, expressed as decimal (.5 used for sample size needed)

c = confidence interval, expressed as decimal (e.g., .01=±1)

Sample size= $[(2.58^2)(.5)(.5)]/(.1^2)=166$ subjects

For effect size, we expect a Cos d medium effect of 0.5. The estimate for sample sizes was obtained by using the first set of pain scores obtained in the PACU. A previous study of 45 patients undergoing knee arthroplasty treated with a femoral nerve block reported a mean visual analog scale score of 3.6 (SD 1.1) upon movement, at 24 h (Singelyn et al. 1998). In an earlier study on total knee arthroplasties (Axelsson et al. 2005), the mean morphine consumption over 48 hours postoperatively was 64.6 (SD 36.3) mg in the placebo group.

The aim of this study was to investigate whether the IPACK technique could reduce the morphine consumption. The Mann-Whitney U test will be used for the analysis of the primary endpoint (morphine consumption). Mann-Whitney U test will be used to assess pain scores and the Bonferroni-Holm method was used to correct for multiple measures. Hospital stay, time to fulfill discharge criteria, knee function scores, and patient satisfaction scores will be analyzed using the Mann-Whitney U test. Dichotomous data will be analyzed using the chi-squared test or Fisher's exact test, as appropriate. Values of p < 0.05 were considered to be statistically significant.

d) Study Timelines

2017-2018 and subsequent data analysis. The subject's participation will be from time of enrollment in the pre-operative period until first 24 hours after surgery. Estimated date of enrollment completion will be when 200 eligible subjects are enrolled in final data analysis. Estimate date for study completion will be June 2018.

 Mount Sinai	Protocol Name:	COMPARISON BETWEEN IPACK BLOCK AND PERIARTICULAR INFILTRATION IN TOTAL KNEE ARTHROPLASTY - A RANDOMISED CONTROLLED TRIAL
	Principal Investigator:	[name] [name].
	Primary Contact Name/Contact Info:	[name] MD. [REDACTED]
	Date Revised:	7/22/2017
	Study Number:	IF# 2087568 , GCO#17-04304

e) Endpoints

The primary endpoints will be the amount of opioid consumption (in mg IV morphine equivalents) postoperatively up to 24 hours after the surgery.

f) Procedures Involved in the Human Research

Prospective randomized controlled trial and data analysis only. IPACK block and PAI. Intraoperative care of the patient will be provided by an anesthesia team member who is a part of the Mount Sinai System. The anesthesia provider will not be aware of the randomization of the patient. Standard post-operative orders will be written for patients during their time in the PACU.

g) Specimen Banking

N/A

h) Data Management and Confidentiality

Data collected in excel file to be de-identified after initial collection. Excel file be subsequently encrypted and shared only between the above listed investigators via secure Mt. Sinai (chpnet) electronic mail. The information included in the data will be medical record number, age, gender, ASA class, type of surgery, pain score assessments, and time to first narcotic, total narcotic use and satisfaction/pain scores during the first 24 hours after surgery. Pain scores on arrival and discharge from PACU, PACU length of stay, location of pain, and ambulation distance with assistance on POD 1 as assessed by PT and activities of daily living (ADL's) on POD 1 as assessed by OT will be other data collected.

Only the research personnel will have access to the data. The data will be stored as a hard copy files and on a secure spreadsheet. The research personnel is responsible for the receipt of the data. The PI will keep the hard copies secure and any electronic data will be encrypted. No personal identifiers will be used. The data will undergo statistical analysis

 Mount Sinai	Protocol Name:	COMPARISON BETWEEN IPACK BLOCK AND PERIARTICULAR INFILTRATION IN TOTAL KNEE ARTHROPLASTY - A RANDOMISED CONTROLLED TRIAL
	Principal Investigator:	[name] [name].
	Primary Contact Name/Contact Info:	[name] MD. [REDACTED]
	Date Revised:	7/22/2017
	Study Number:	IF# 2087568 , GCO#17-04304

i) Provisions to Monitor the Data to Ensure the Safety of Subjects

Part I: Elements of Data and Safety Monitoring Plan

MSSM Principal Monitor:

Last Name: [name]

First Name: [name]

Academic Title: Attending Physician, Assistant Professor

Department: Anesthesiology

Mailing Address: Mount Sinai West [name]

[contact]

Fax:

E-mail: [contact]

MSSM Additional Monitor:

Last Name: [name]

First Name: [name]

Academic Title: Research Personnel, Physician

Department: Anesthesiology

Mailing Address: Mount Sinai West [name]

[contact]

Fax:

E-mail: [contact]

The principal monitor is a board certified anesthesiologist thus minimizing the risk to the subjects and further optimizing their health and wellbeing. Adverse events will be monitored as a standard of care everyone receives regardless of participation in the study. The safety and data information will be reviewed on a daily basis until the desired sample size is achieved. All temporary and/or permanent suspensions will be reported.

[name] MD – Roles for [name] include serving as primary research coordinator involved in data collection, subject recruitment, manuscript writing and preparation, data analysis, safety monitoring, and responding to adverse events and/or complications. She has completed all of her required CITI training to be IRB certified and has experience in clinical research. In addition she has been a resident physician in anesthesiology with the Icahn School of Medicine in good standing for the previous three years going on her fourth.

 Mount Sinai	Protocol Name:	COMPARISON BETWEEN IPACK BLOCK AND PERIARTICULAR INFILTRATION IN TOTAL KNEE ARTHROPLASTY - A RANDOMISED CONTROLLED TRIAL
	Principal Investigator:	[name] [name].
	Primary Contact Name/Contact Info:	[name] MD. [REDACTED]
	Date Revised:	7/22/2017
	Study Number:	IF# 2087568 , GCO#17-04304

j) Withdrawal of Subjects

Patients may withdraw from the study at any given time by contacting any member of the research study group. Data will not be collected on patients who wish to withdraw. Patient do not need to withdraw consent in writing.

6) Risks to Subjects

If patients are injured or made sick from taking part in this research study, medical care will be provided. Generally, this care will be billed to the patient or their insurance in the ordinary manner and the patient will be responsible for all treatment costs not covered by insurance, including deductibles, co-payments and coinsurance. This does not prevent the patient from seeking payment for injury related to malpractice or negligence. Contact the investigator for more information.

As with any medication, there is a possibility of an allergic reaction. Although rare, possible complications include LA toxicity, hypersensitivity reaction, bleeding or local site infection, chance of pneumothorax. All anesthesiologists involved in patient care will be prepared for the prevention and rescue for any complications involving local anesthetic injections.

7) Provisions for Research Related Harm/Injury

If patients are injured or made sick from taking part in this research study, medical care will be provided. Generally, this care will be billed to the patient or their insurance in the ordinary manner and the patient will be responsible for all treatment costs not covered by insurance, including deductibles, co-payments and coinsurance. This does not prevent the patient from seeking payment for injury related to malpractice or negligence. Contact the investigator for more information.

8) Potential Benefits to Subjects

It is important to know that you may not get any benefit from taking part in this research. Others may not benefit either. However, possible benefits may be improved knowledge about how the different forms of analgesia affect pain control in knee surgery. There is potential for better pain control after the surgery.

 Mount Sinai	Protocol Name:	COMPARISON BETWEEN IPACK BLOCK AND PERIARTICULAR INFILTRATION IN TOTAL KNEE ARTHROPLASTY - A RANDOMISED CONTROLLED TRIAL
	Principal Investigator:	[name] [name].
	Primary Contact Name/Contact Info:	[name] MD. [REDACTED]
	Date Revised:	7/22/2017
	Study Number:	IF# 2087568 , GCO#17-04304

9)Provisions to Protect the Privacy Interests of Subjects

Patients will be appropriately educated about the research study. Any questions or concerns they have will be adequately addressed and patients will have the option to decline participation. Patients will be given as much time as they need to review the consent form. The study personnel will be approaching the subjects. Privacy will be maintained by not including any identifiers such as names or addresses in the data collected.

The identities of human subjects whose data is being studied will be de-identified as per HIPAA Privacy Rule.

10)Economic Impact on Subjects

Patients will not incur any additional cost for participating in the study. The medications used are part of a standard anesthetic regimen that will be billed to subject's insurance as bundled standard of anesthesia care. The cost of the procedure is overall unaffected.

11)Payments to Subjects

Patients will not be reimbursed for their participation.

12)Consent Process

Informed consent will be obtained prior to the procedure. Both the HRP-090 (SOP) Informed Consent Process for Research and the HRP-091 (SOP) Written Documentation of Consent will be followed by the study team. These documents are both available at <http://icahn.mssm.edu/research/resources/program-for-the-protection-of-human-subjects/irb-members-palette>.

Mount Sinai	Protocol Name:	COMPARISON BETWEEN IPACK BLOCK AND PERIARTICULAR INFILTRATION IN TOTAL KNEE ARTHROPLASTY - A RANDOMISED CONTROLLED TRIAL
	Principal Investigator:	[name] [name].
	Primary Contact Name/Contact Info:	[name] MD. [REDACTED]
	Date Revised:	7/22/2017
	Study Number:	IF# 2087568 , GCO#17-04304

13. Process to Document Consent in Writing

The patients will receive a paper copy of the IRB approved consent packet and will sign in the designated areas to confirm consent of participation. They will have the option of have a copy of the consent and may ask for a personal copy of the consent.

14. Vulnerable Populations

Indicate specifically whether you will include (target) or exclude each of the following populations:

I n c l u d e	E x c l u d e	Vulnerable Population Type
	X	Adults unable to consent
	X	Individuals who are not yet adults (e.g. infants, children, teenagers)
	X	Wards of the State (e.g. foster children)
	X	Pregnant women
	X	Prisoners

15. Multi-Site Human Research (Coordinating Center)

This study will be performed within the Mount Sinai West and St. Luke's Hospitals. No additional centers will be involved.

 Mount Sinai	Protocol Name:	COMPARISON BETWEEN IPACK BLOCK AND PERIARTICULAR INFILTRATION IN TOTAL KNEE ARTHROPLASTY - A RANDOMISED CONTROLLED TRIAL
	Principal Investigator:	[name] [name].
	Primary Contact Name/Contact Info:	[name] MD. [REDACTED]
	Date Revised:	7/22/2017
	Study Number:	IF# 2087568 , GCO#17-04304

16. Community-Based Participatory Research

This does not apply to our study.

17. Sharing of Results with Subjects

Results will not be shared with the patients since the study will take time to complete. Patients can request results if they contact the PI by writing.

18. External IRB Review History

This does not apply to our study.

19. Control of Drugs, Biologics, or Device

Not applicable. Local anesthetic are routinely used in this setting.

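### Section 1 makes PACU pain scores primary alongside 24-hour opioid use, Sections 5c and 5e name opioid use alone, and the Holm family is not listed

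*Combined protocol and SAP*

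**What the plan says.** Under its primary-outcome heading, Section 1 lists opioid consumption in IV morphine equivalents "during the first 24 hours after the procedure. VAS pain scores on arrival and departure from PACU". The secondary heading then takes up VAS only from the floor onward: "The degree of postoperative pain in terms of VAS scores from arrival to the floors to the first 24 hours after surgery". The pain scores are thus divided at PACU departure, with the earlier two primary and the later ones secondary.

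Other sections give a different hierarchy:

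- **Section 5e:** "The primary endpoints will be the amount of opioid consumption (in mg IV morphine equivalents) postoperatively up to 24 hours after the surgery".
- **Section 5c, aim:** "The aim of this study was to investigate whether the IPACK technique could reduce the morphine consumption".
- **Section 5c, analysis:** "The Mann-Whitney U test will be used for the analysis of the primary endpoint (morphine consumption"), in the singular.
- **Section 5h, data list:** "Pain scores on arrival and discharge from PACU, PACU length of stay, location of pain, and ambulation distance with assistance on POD 1" appear together among the other data to be collected, so PACU scores sit with items that Section 1 calls secondary.

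Two statements point back towards pain scores. The purpose statement before Section 1 describes quality of analgesia "performed by surgeon as measured by patient's opioid consumption and pain scores". Section 5c also says the sample-size estimate was based on the first PACU pain scores.

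On multiplicity, Section 5c says only this: "Mann-Whitney U test will be used to assess pain scores and the Bonferroni-Holm method was used to correct for multiple measures". The significance threshold is p < 0.05.

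**The concern.** The plan does not fix in advance what makes the trial positive. A team that finds a PACU VAS difference and no opioid difference could cite Section 1. A team that finds the reverse could cite 5e. No rule states whether one primary result is enough or all are needed, so the choice could be made after the data are seen.

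The Holm sentence does not close this gap. It concerns pain scores, does not say which ones, and does not include opioid use, which has its own test in a separate sentence. Holm then limits error among the pain scores, but not across opioid use and pain scores together. If either could carry a primary claim, the overall error exceeds 5%. If all had to succeed, error would be controlled but power would fall.

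**Working it through.** **The plan's own figure.** Section 5c gives Z²·p·(1−p)/c² with Z = 2.58, p = 0.5, c = 0.10:

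2.58² × 0.25 / 0.01 = 166.4, which matches the stated 166 (rounded up to 200).

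The formula uses neither pain nor opioid data, so the sample size does not reveal which outcome is primary. It also does not fit the statement that the estimate came from PACU pain scores.

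**Inputs from the plan.** Threshold 0.05, 200 patients, standardised effect 0.5 (all 5c); three measures under the primary outcome (Section 1); Holm for pain scores (5c).

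**Inputs assumed, because the plan does not give them.** Two-sided tests; 100 per arm; a Holm family of m = 2 to 8 pain scores, two of them the PACU scores; test statistics equally correlated at 0 to 0.7; Mann-Whitney efficiency 0.955 relative to the t-test.

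**Error if either result counts.** Opioid use is tested at 0.05 and the pain scores by Holm at 0.05. Under independence with no true differences, the chance that opioid use or a PACU score is falsely significant is approximately

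1 − 0.95 × (1 − 0.05/m)²

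- m = 2: 1 − 0.95 × 0.975² = 9.7%
- m = 3: 8.1%
- m = 4: 1 − 0.95 × 0.9875² = 7.4%
- m = 6: 6.6%
- m = 8: 1 − 0.95 × 0.99375² = 6.2%

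Simulation of correlated normal test statistics with the full Holm procedure gives the ranges below. The left end of each range is correlation 0 and the right end is 0.7. The VAS-only column is the either-counts figure less the 5% for opioid use.

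| Pain scores in Holm family | False primary claim, either counts (%) | Of which VAS positive, opioid negative (%) | Power if all three must succeed (%) |
|---|---|---|---|
| 2 | 9.7 to 7.7 | 4.7 to 2.7 | 80.8 to 86.2 |
| 3 | 8.2 to 6.7 | 3.2 to 1.7 | 80.2 to 84.9 |
| 4 | 7.4 to 6.2 | 2.4 to 1.2 | 79.1 to 83.8 |
| 6 | 6.6 to 5.8 | 1.6 to 0.8 | 77.4 to 81.5 |
| 8 | 6.2 to 5.5 | 1.2 to 0.5 | 75.5 to 79.9 |

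The 9.7% is the maximum over the correlations examined. The bound under any dependence is 0.05 + 0.05 = 10%.

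**Power.** For opioid use alone, 0.5 × √(100 × 0.955 / 2) = 3.455, and Φ(3.455 − 1.960) = 93.3%. The last column of the table requires opioid use and both PACU scores to be significant, with the pain scores under Holm and an effect of 0.5 on every measure. Error under that rule cannot exceed 5%, because each test is at 0.05 or stricter.

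**If opioid use is the sole primary.** The error is 5%.

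**The case against.** The strongest reply is that the operative text already settles the matter. Section 5c contains the only analysis text and names one primary endpoint, and 5e, the endpoints section, agrees. On that reading the error is 5% and Section 1 merely needs tidying. This is the likelier reading. It is not a specification, however: Section 1 assigns the primary label explicitly and divides the VAS scores to do so, and the purpose statement and the sizing sentence give that label some support.

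A second reply is that the correction for multiple measures could have been meant to cover opioid use and both PACU scores together. Error would then be at most 5% (simulated 4.9% at correlation 0 and 3.9% at 0.7). The sentence is about pain scores, though, and opioid use is handled elsewhere, so the text does not support relying on this.

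A third reply is that the extremes overstate the problem, and this is fair in part. The 9.7% needs a family of only the two PACU scores, although 5c refers to pain scores without restriction. The 75% needs an eight-score Holm family on top of an all-must-succeed rule. With each of the three tested at 0.05 and no Holm, power would be 81% to 87%. The Section 5h list is also only a data inventory and is weak evidence on endpoint status.

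Finally, demoting PACU VAS is not the only valid remedy. Co-primary endpoints with a stated success rule would also resolve the contradiction.

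**Conclusion.** The concern holds. Sections 1, 5c and 5e disagree on what is primary, no success rule is given, and the Holm family is undefined. The numerical inflation is modest on the more natural family sizes: 0.5 to 2.4 percentage points above 5% with 4 to 8 pain scores, rising to 4.7 points with two. It arises only if either result counts and Holm covers pain scores alone. If all three must succeed, the loss is about 7 to 18 points of power (93.3 − 86.2 = 7.1; 93.3 − 75.5 = 17.8). These figures depend on the assumed family size, correlation, two-sided testing and equal allocation. The contradiction itself depends on none of them. It should be corrected before analysis because it leaves the definition of a positive trial open.

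**What to change.** - **Section 1:** name one primary endpoint, total IV morphine equivalents in the first 24 hours after surgery, as the sole basis for calling the trial positive. Move VAS at PACU arrival and departure to secondary.
- **Section 5c:** state that the primary test is a Mann-Whitney test at two-sided 0.05 (the plan does not give sidedness, so this is an addition). List PACU arrival, PACU departure and each floor VAS time point to 24 hours as one Holm family at 0.05.
- **Section 5c, sizing sentence:** delete or reconcile the statement that the size was estimated from first PACU pain scores, since the displayed formula does not use them. Re-deriving the sample size is a separate matter.
- **Section 5e:** already names opioid use alone and can stay.

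The cost is wording in two sections, with no change to sample size or data collection. The floor VAS time points are not given anywhere, so the team must write down which ones it will analyse. The one real loss is that a benefit confined to the PACU could be reported only as a secondary result. If the team wants PACU VAS to remain primary, it must instead state the success rule and the matching error control.

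### The plan lists the surgeon as blinded, yet the surgeon gives the infiltration that defines the PAI arm, so the triple-blind label is not supported as written

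*Combined protocol and SAP*

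**What the plan says.** Section 3 (Setting of the Human Research) describes the study as "Prospective triple blinded randomized control trial undergoing total knee arthroplasty surgeries", and section 5 (Study Design) opens with the same label: "Prospective triple blinded randomized control trial". The only place that names three blinded parties is later in section 5: "Otherwise, the patient, surgeon, and anesthesiologist in the case will be blinded".

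On how the two treatments are given, section 5 says:

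- "Block team will perform all blocks". The IPACK group receives its injection under ultrasound guidance.
- At the end of surgery, before the skin is closed, "all patients in the PAI group will receive 100cc of joint cocktail infiltrated by the surgeon".
- One element is common to the two arms: "Patients in both groups will receive a post operative adductor canal catheter in the PACU".
- One person outside the blinded list is mentioned: "Resident anesthesiologist will know the group allocation but will not be involved in the study".

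Section 5(f) adds that whoever provides intraoperative anesthesia care will not know the randomization.

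On outcome assessment, the only sentence that may bear on blinding is in section 5: "Once recruited blinding assessments will be done by the study team". Sections 1 and 5(h) name physical therapy and occupational therapy as assessors of the first-day functional outcomes and say nothing of their blinding. Section 4 gives both the principal investigator and the research coordinator the tasks of data collection and data analysis, again without a blinding statement.

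**The concern.** One treatment under comparison is something the surgeon does with their own hands. Unless the surgeon performs an indistinguishable act in the other arm, giving or not giving the infiltration reveals the allocation. A report that repeats the triple-blind label, with the surgeon as one of the three, would claim a protection the design does not have.

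The endpoints are open to influence from people who know the arm. Opioid consumption over 24 hours and VAS pain scores depend on what patients report and how staff respond. The adductor canal catheter runs within a rate range, and the plan does not say who sets the rate or whether that person lacks the allocation. The surgeon is nowhere said to record pain scores or opioid totals, so the route is indirect: knowledge of the arm can pass to the patient or to the staff who treat and assess. Readers therefore need to know whether those who recorded the outcomes lacked the allocation.

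**Working it through.** The plan gives no figure for blinding to reproduce, so the check sets its statements side by side.

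**Step 1: the surgeon.** Section 5 puts the surgeon on the blinded list and, in the same paragraph, has the surgeon infiltrate every PAI patient. For the IPACK group it describes a block by a separate team and no infiltration, real or dummy. The act is therefore present in one arm and absent in the other, and the surgeon knows the arm by skin closure at the latest. The plan does not say whether the surgeon learns it sooner. With 200 patients planned (section 5(c)), this applies to 200 of 200. That counts known allocations and is not a measure of bias.

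**Step 2: the other two named parties.**

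| Party named as blinded | Described support | Gap |
|---|---|---|
| Patient | Separate block team; same catheter in both groups | No sham block or sham infiltration described |
| Case anesthesiologist | Separate block team; resident who knows the allocation is kept out of the study; section 5(f) states unawareness | Infiltration takes place during this person's intraoperative care, with no described way to conceal it |
| Surgeon | None | Contradicted by the same paragraph |

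Of the three, one is contradicted and 3 − 1 = 2 have at most partial support. The gaps for those two do not show that their blinding fails.

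**Step 3: the label.** The plan does not define the three parties behind the triple-blind label. If they are the three in section 5, the label is unsupported because one of them knows the arm. If another set was meant, such as patient, assessor and analyst, the plan never says so.

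**Step 4: outcome recorders and analyst.** Section 1 lists 2 primary items (24-hour opioid consumption; PACU pain scores, with arrival and departure counted as one) and 6 secondary items (pain scores from the floor to 24 hours, time to first narcotic, PACU length of stay, location of pain, walking distance, activities of daily living), so 2 + 6 = 8.

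- Items that name an assessor: 2 of 8 (walking distance by physical therapy, activities of daily living by occupational therapy).
- Items with a clear statement that the recorder lacks the allocation: 0 of 8.

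The sentence on assessments by the study team can mean blinded outcome assessment or a check of blinding. On neither reading does it say which outcomes or which recorders it covers. Two people hold both collection and analysis roles, and coded arms are not mentioned. The resident who knows the allocation is to stay outside the study, while section 4 describes the research coordinator as an anesthesiology resident. Nothing suggests they are the same person, but their separation is not stated.

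**The case against.** The best defence of the sentence is its first word, *Otherwise*. It follows the description of the resident who knows the allocation and of the surgeon's infiltration, so it could mean that blinding applies apart from what those steps reveal. That would make it poor drafting rather than a wrong claim. The reading does not rescue the text, because the surgeon is still on the blinded list. If the surgeon was meant to be excepted, the sentence says the opposite and must be corrected anyway.

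It is also fair to say that the plan never states outright that only the PAI group is infiltrated. This is an inference from the absence of any infiltration, real or dummy, in the IPACK group's description. It is a strong inference, and nothing elsewhere in the plan weakens it.

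A third objection is that the consequence is modest. The surgeon does not record the endpoints, the infiltration itself comes only at the end of surgery, and section 5(f) provides for standard postoperative orders in the PACU, which limits the scope for differential care there. These points stand and are why the risk is called indirect. They do not make the statement about the surgeon true, and the PACU provision does not cover the rest of the 24 hours or say who writes the orders.

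Finally, the plan never promises a coded-arm analysis, so asking for one adds a safeguard rather than repairing a contradiction. That is correct, and the conclusion does not depend on it.

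**Conclusion.** The concern holds. The statement that the surgeon is blinded is contradicted by the paragraph that contains it, and as written the surgeon knows the arm of all 200 planned patients. This must be corrected because it misstates a core design safeguard.

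Three conclusions are more limited:

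- The triple-blind label is unsupported on the condition that its parties are the three named in section 5, the only trio the plan offers.
- Blinding of the patient and case anesthesiologist is asserted with partial support; failure is not shown.
- Blinding of outcome recorders and of the analyst is not clearly stated.

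The conclusion assumes that the IPACK group receives no infiltration by the surgeon, real or dummy, as the available text implies. The size and direction of any bias cannot be computed from the documents.

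**What to change.** 1. In section 5, remove the surgeon from the list of blinded parties and state that the surgeon and the block team are not blinded.
2. In sections 3 and 5, replace the triple-blind label with a list of the parties actually blinded and the measure that supports each. Align the sentence on the anesthesia provider in section 5(f) with that list.
3. Clarify whether the study team's assessments are blinded outcome assessments or a check of blinding, and whom they cover. State that the resident who knows the allocation has no data collection or analysis role.
4. Require that pain scores, 24-hour opioid totals and the physical and occupational therapy outcomes be recorded by existing staff without the allocation, never by the surgeon or block team, and that the primary analysis be run on coded arms.

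The cost is revised wording in sections 3 and 5 and an assignment of recording tasks among existing staff. The description of blinding becomes less favourable, and the investigator must confirm that enough existing staff lack the allocation. Neither the treatments nor the sample size change.
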